8.8 Pregnancy test

All pregnancy test results for women will be listed by age group, patient and visit.

9 Statistical methods for Biomarker data

Commercially Confidential Information

1.1 Scope of document

The RAP documents contain detailed information to aid the production of Statistics & Programming input into the Clinical Study Report (CSR) for trial “CCDZ173X2201-Part II”.

The Statistical analysis plan (SAP) describes the implementation of the statistical analysis planned in the protocol

1.2 Study reference documentation

This Statistical Analysis Plan is based on the amended protocol v10 dated 13th-Oct-2020.

1.3 Study objectives

This study is designed to evaluate CDZ173, a selective PI3K δ inhibitor, in patients with genetically activated PI3K δ , i.e., patients with APDS/PASLI. The study consists of two parts. Part I is now complete and was the open label part designed to establish the safety and pharmacokinetics of CDZ173 in the target population, as well as to select the optimal dose to be tested in Part II. Part II is the subject, investigator and sponsor-blinded, randomized part designed to assess efficacy and safety of CDZ173 in this population.

This SAP focuses on Part II only.

1.3.1 Part II

1.3.1.1 Primary Objective(s)

- To assess the clinical efficacy (lymphadenopathy and immunophenotype normalization) of CDZ173 in patients with APDS/PASLI

1.3.1.2 Secondary Objective(s)

- To assess the effect of CDZ173 on lymphadenopathy (non-index lesions and spleen)
- To assess the pharmacokinetics of CDZ173 in patients with APDS/PASLI
- To assess the efficacy of CDZ173 to modify health-related quality of life in patients with APDS/PASLI
- To assess the efficacy of CDZ173 by the Physician's Global Assessment (PGA) and the Patient's Global Assessment (PtGA)
- To assess biomarkers reflecting the efficacy of CDZ173 to reduce systemic inflammatory components of the disease
- To assess the treatment benefit to individual patients
- To assess the safety and tolerability of CDZ173 in patients with APDS/PASLI

1.3.1.3 Exploratory Objective(s)

Commercially Confidential Information

1.3.1.4 Objective for gender split analysis

- To assess whether there is comparable efficacy and tolerability/safety of CDZ173 (70 mg b.i.d.) after 12 weeks of treatment for men and women.

[figure not shown]
1.4 Study design and treatment

1.4.1 Part II

Part II is the randomized, subject, investigator and sponsor-blinded, placebo-controlled, fixed dose part investigating approximately 30 patients with APDS/PASLI ([Figure 1-1](#)). Since the primary endpoint (SPD) requires imaging by either MRI or CT, which results in patients being exposed to radiation, the design is planned factoring these measurements in.

The CDZ173 dose to be used in this part is selected based on safety, tolerability, PK and PD data from Part I.

Figure 1-1 Study Design Part II

During the Screening Visit (Day -50 to Day -2) patients' eligibility will be assessed and then reviewed during the Baseline Visit.

Patients who are deemed eligible for enrollment into the study based on the inclusion/exclusion criteria will attend the clinic on Day -1 for baseline assessments.

On Day 1 patients will be randomly allocated to one of the two treatment groups in a 2:1 ratio to receive either 70 mg CDZ173 b.i.d. or matching placebo for a twelve week period in a patient, investigator and sponsor blind fashion.

Patients enrolled in Part I of the study will not participate in Part II, i.e. new patients will be selected.

For the patients who do not directly roll over from Part II to treatment in the extension study [\[CCDZ173X2201E1\]](#), the following applies:

During the four weeks after the last day of dosing the patients will be followed-up for safety. On Day 112 patients will undergo the end of study visit.

Patients who discontinued study treatment prematurely will perform an early treatment discontinuation visit (named V104.1) as soon as possible after their treatment discontinuation. The assessments scheduled for this visit are the ones marked with a * in Table 8-2 of the study protocol.

If the premature discontinuation from study treatment happens before the scheduled V104, the patients will be asked to also return at Day 85, and complete the Visit 105 (without further imaging assessments to avoid additional radiation). This will be considered their last Visit.

If on the other hand the premature discontinuation from study treatment happens at or after the scheduled V104, the patients will in addition to the early treatment discontinuation visit be asked to perform the EOS visit 4 weeks after the treatment discontinuation visit. This will be considered their last Visit.

2 First interpretable results (FIR)

Commercially Confidential Information

3 Interim analyses

Not applicable.

4 Statistical methods: Analysis sets

For all analysis sets, patients will be analyzed according to the study treatment received.

The safety analysis set will include all patients that received any study drug.

The PK analysis set will include all patients with at least one available valid (i.e. not flagged for exclusion) PK concentration measurement, who received any study drug and experienced no protocol deviations with relevant impact on PK data.

The PD analysis set will include all patients who received any study drug and with no protocol deviations with relevant impact on PD data.

The key safety and efficacy endpoints will also be reported by age group determined at Screening visit (≥ 18 years old and < 18 years old).

The analysis sets and protocol deviation codes are related as follows:

Table 4-1 Protocol deviation codes and analysis sets

Category Deviation code	Text description of deviation	Data exclusion
	Subjects are excluded from PK analysis in case of these PDs:	Exclude subject from PK analysis set
INCL01	Written informed consent was not obtained before any study assessment was performed	Yes

Commercially Confidential Information

	Subjects are excluded from PD analysis in case of these PDs:	Exclude subject from PD analysis set
INCL01	Written informed consent was not obtained before any study assessment was performed	Yes

Commercially Confidential Information

Category Deviation code	Text description of deviation	Data exclusion
Comercially Confidential Information		
Subjects are excluded from PK and PD analysis in case of these PDs: INCL01	Written informed consent was not obtained before any study assessment was performed	Exclude subject from PK and PD analysis sets Yes
Comercially Confidential Information		

5 Statistical methods for Pharmacokinetic (PK) parameters

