6.1.1 Investigational treatment

The investigational drug, CDZ173 10 and 70 mg capsules and matching placebo capsules will be prepared by Novartis and supplied to the investigator site as open label patient-specific packs for Part I and blinded patient specific packs for Part II.

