11.1 Analysis sets

For all analysis sets, patients will be analyzed according to the study treatment(s) received.

The full analysis set will include all patients that received any study drug.

The safety analysis set will include all patients that received any study drug.

The PK analysis set will include all patients with available PK data and no protocol deviations with relevant impact on PK data.

The PD analysis set will include all patients who received any study drug and with no protocol deviations with relevant impact on PD data.

In Part II, the key safety and efficacy endpoints will also be reported by age group (≥ 18 years old and < 18 years old).

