11.4 Analysis of the primary variable(s)

The primary aim of Part I, along with assessing safety and tolerability, was to determine a dose to be used in the confirmatory Part II. The primary aim of Part II is to assess efficacy of CDZ173 at the selected dose (70 mg b.i.d.) after 12 weeks of treatment.

In Part I, phosphorylated Akt from unstimulated B cells was quantified at baseline and at the end of the 4-week treatment period with each of the three dose levels. The lowest dose level (up to 70 mg b.i.d.) leading to normalization of the unstimulated pAkt in B cells to healthy volunteer levels should be carried into Part II for generation of confirmatory data, but *ex vivo* stimulated pAkt in B cells and other variables may also be taken into account for the selection of the dose.

In Part II, lymphadenopathy will be measured by the SPD of index lesions (selected as per the Cheson methodology ([Cheson et al 1999](#)) from MRI/CT imaging) and immunodeficiency will be measured by percentage of naïve B cells out of total B cells. The co-primary endpoints are the change from baseline in the log10 transformed SPD of index lesions and the change from baseline in the percentage of naïve B cells out of total B cells at the end of treatment.

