11.6 Sample size calculation

In Part I

The sample size for Part I (6 patients) was mainly based on feasibility, while still providing adequate precision to identify an appropriate dose for Part II.

Commercially Confidential Information

In Part II

For Part II, the sample size (20 patients in active and 10 patients in placebo for a total of 30 patients) is mostly driven by the analysis of one of the two co-primary efficacy variables, the change from baseline in the log10-transformed SPD of index lesions.

Commercially Confidential Information

Assuming that 10% of patients are excluded from the analysis of the other co-primary variable, the change from baseline in the percentage of naïve B cells out of total B cells, due to no reduced percentage of naïve B cells at baseline, it is anticipated that 27 patients will provide data for the analysis. Assuming an increase of 25% points and comparable variability as in Part I for the change from baseline to 12 weeks in the percentage of naïve B cells (standard deviation of 14), with 27 patients this part of the study will have 98% power to detect a statistically significant p-value at the 5% level.

With the above assumptions, the power to achieve a statistical significance in both endpoints is at least 78%.

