6.1.4 Statistical model, assumptions and hypotheses

An analysis of covariance will be performed to compare the change of the log10 transformed SPD from baseline between the two treatment groups, with treatment as a fixed effect and log10 transformed baseline SPD as a covariate. The baseline intake of glucocorticoids as well as the information about being treated with intravenous immunoglobulin G (IgG) will both be included as categorical (Yes/No) covariates. The comparison of the two treatment groups will be two-sided, with a 5% type I error. Patients with zero lesions at baseline will be excluded from the analysis.

Commercially Confidential Information

An analysis of covariance will be performed to compare the change from baseline in the naïve B cells at the end of treatment (i.e. Day 85 assessment for patients who complete the 12 week treatment period or the treatment discontinuation visit for patients who discontinue treatment prematurely prior to Day 85 visit) between the two treatment groups, adjusted for baseline naïve B cells frequencies. The use of glucocorticoids and intravenous IgG at baseline will both be included as categorical (Yes/No) fixed effects. Comparison of the two treatment groups will be two-sided, with a 5% type I error. Only patients with a reduced percentage of naïve B cells at baseline (defined as below 48 % van Gent et al 2009) will be included to the analysis. Baseline

Commercially Confidential Information

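### Efficacy is grouped by treatment received in every analysis set, with no visible as-randomised exception for the randomised Part II comparison

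*SAP*

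**What the plan says.** Protocol 11.1 opens with one rule: "For all analysis sets, patients will be analyzed according to the study treatment(s) received". Part II SAP section 4 repeats it: "For all analysis sets, patients will be analyzed according to the study treatment received". Both rules cover every set.

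Protocol 11.4 describes the aim of Part I by saying that it "was to determine a dose to be used in the confirmatory Part II", so the randomised Part II is meant to confirm efficacy. Its co-primary tests are two-sided at 5%.

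On membership, Protocol 11.1 defines an efficacy-type set: "The full analysis set will include all patients that received any study drug". The visible text ties that set to no analysis, and the visible Part II SAP does not list it. The SAP lists safety, PK and PD sets, and defines the last as follows: "The PD analysis set will include all patients who received any study drug and with no protocol deviations with relevant impact on PD data".

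The SPD model in SAP 6.1.4 begins "An analysis of covariance will be performed to compare the change of the log10 transformed SPD from baseline between the two treatment groups". The visible text of 6.1.4 and 6.1.4.2 then limits each co-primary model by data and baseline status: values at baseline and at end of treatment, at least one baseline lesion for SPD, and naïve B cells below 48% at baseline for the other endpoint. It names no analysis set.

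**The concern.** A randomised comparison is protected by keeping each patient in the arm that chance assigned. Grouping by treatment received gives that up whenever the treatment taken differs from the treatment assigned. It is the usual choice for safety and PK, but as written it also governs the two confirmatory tests. With a planned 20 and 10 patients, one reassigned patient is a visible share of an arm.

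A second, weaker matter follows. SAP 5.2 names the PK set for PK and SAP section 7 names the safety set for safety. In the primary-efficacy section the only set visibly named is the PD set, for individual profile plots (6.1.4.3). That set drops patients for some deviations. A programmer could carry it into the co-primary models and so remove patients after randomisation.

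**Working it through.** **Inputs.** From Protocol 11.6: 20 active and 10 placebo patients; 27 expected in the naïve B cell analysis; difference 25 points; SD 14; stated power 98%; and, for the two endpoints jointly, "With the above assumptions, the power to achieve a statistical significance in both endpoints is at least 78" per cent. Assumed: the 27 split 18 to 9, in line with 2:1 allocation; all 30 enter the SPD analysis; exactly one dosing error. The documents give no error rate.

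**The plan's own figure.** SE = 14 × √(1/18 + 1/9) = 5.72. Noncentral t power for a difference of 25 with 25 df is 98.7%, which agrees with the stated 98%.

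**SPD effect size.** Its assumptions are redacted, so it is back-calculated. The lower bound for joint power is 80% + 98% − 100% = 78%, which implies 80% for SPD. Under independence it would be 78/98 = 79.6%. With 20 and 10 patients, 80% power needs a standardised difference of 1.124 (1.118 for 79.6%). SE in SD units = √(1/20 + 1/10) = 0.387.

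**How far one regrouped patient moves the estimate.** Suppose there is no true effect and the patient lies z SD from the others.

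- Naïve B cells, active patient given placebo: 14z × (1/18 + 1/10) = 2.18 points at z = 1 and 4.36 at z = 2.
- Naïve B cells, placebo patient given active: 14z × (1/9 + 1/19) = 2.29 and 4.58 points. Over both directions the shift is 0.38 to 0.80 SE.
- SPD: z × (1/20 + 1/11) = 0.141 and 0.282 SD; z × (1/10 + 1/21) = 0.148 and 0.295 SD. Over both directions the shift is 0.36 to 0.76 SE.

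A shift of this size can fall either way. It is not a bias unless the error is related to outcome.

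**Type I error.** In 200,000 simulated trials per case (two-sample t-test, no true effect, error unrelated to outcome), the rejection rate was about 5% for both endpoints, both directions of error and both groupings.

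**Power with one error.** Same simulation, with the patient responding to the drug actually taken:

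| Endpoint | No error | Error | As randomised | As received |
|---|---|---|---|---|
| Naïve B cells | 98.8% | active given placebo | 97.1% | 99.1% |
| Naïve B cells | 98.8% | placebo given active | 95.1% | 98.3% |
| SPD (d = 1.124) | 80.0% | active given placebo | 74.5% | 81.8% |
| SPD (d = 1.124) | 80.0% | placebo given active | 69.9% | 77.8% |

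The as-randomised loss comes from dilution. For naïve B cells the mean difference falls to 25 × (1 − 1/18) = 23.6 or 25 × (1 − 1/9) = 22.2 points. For SPD it falls to 1.124 × (1 − 1/20) = 1.07 or 1.124 × (1 − 1/10) = 1.01 SD. One wrongly treated patient also widens the spread within the arm. These are unadjusted t-tests, not the planned covariance models, so they show scale only.

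**The case against.** **The consequence is hypothetical.** Assigned and received treatment differ only after a wrong-arm error. The protocol supplies "blinded patient specific packs for Part II", and section 6.5 requires identical packaging and appearance, so an error related to outcome is unlikely. This stands, and it keeps the point minor.

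**The remedy costs power.** If an error does occur, as-randomised grouping has less power than as-received grouping, by 7 to 8 points for SPD. This also stands. It is the price of keeping the comparison as randomised, and it is paid only if an error occurs.

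**Redaction.** The estimand sections (SAP 6.1.1 and 6.2.1), parts of Table 4-1, parts of SAP 6.1.3, 6.1.4 and 6.2.4, and the protocol's supportive analyses are blacked out. An exception or a named set may be there. This weakens the set-naming matter most, because that rests on silence. The grouping matter rests on an explicit sentence covering all sets, so any exception belongs beside it.

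**Stronger readings to resist.**

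- A reader might infer that the rule inflates type I error. The check shows no inflation for an error unrelated to outcome. A rate clearly away from 5% needs the wrongly treated patient to be picked by eventual outcome, and whether it then rises or falls depends on how that pick is defined. Nothing in the documents supports such a mechanism.
- A reader might infer that the co-primary analyses have no defined population. SAP 6.1.4 and 6.1.4.2 do say who enters each model. The first sentence of SAP 6.2 is circular, but the next one carries the 6.1.4.2 rules to the secondary endpoints. What stays open is whether PD-relevant deviations also exclude patients.
- A reader might think that the protocol's full analysis set is of no use because it too is grouped as received. It does not cure grouping, but it has no deviation-based exclusions, so it would settle membership.

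**Conclusion.** The point holds as a minor one. On the visible text, both documents group every analysis set by treatment received and exempt no efficacy comparison in a trial part that is randomised and confirmatory. Changing this for efficacy is a cheap safeguard. It does not correct a demonstrated bias: with no dosing error the two groupings give identical results, and for an error unrelated to outcome type I error is unaffected. Naming the efficacy set is a clarification, conditional on what the redacted text says. The conclusion about the text needs no numerical assumption. The sizes rest on a single assumed error, an 18 to 9 split, no SPD exclusions, unadjusted tests and a back-calculated SPD effect.

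**What to change.** - In Protocol 11.1 and Part II SAP section 4, state that Part II efficacy analyses use the protocol's full analysis set, that is, randomised patients who took any study drug, grouped as randomised. Apply only the data and baseline restrictions already stated.
- Keep treatment-received grouping for safety and PK.
- If a dosing error occurs, report the as-received grouping as a sensitivity analysis.
- Unless redacted text already does so, name this set in SAP 6.1.4 and 6.2, so that deviations with PD impact do not remove patients from the co-primary models.

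The cost is a few sentences, with no new data or visits. The only downside comes with an actual error. Relative to no error, each one costs about 2 to 4 points of power for naïve B cells (98.8% to 97.1% or 95.1%) and about 5 to 10 points for SPD (80.0% to 74.5% or 69.9%).

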5.1 Variables

The following plasma pharmacokinetic parameters will be determined using the actual recorded sampling times and non-compartmental method(s) with Phoenix WinNonlin (Version 6.2 or higher): Cmax, Tmax, AUC0-8h and AUClast. Other PK parameters may be added as appropriate. After multiple doses, PK will be summarized in terms of trough concentration (Ctrough).

PK parameters will be calculated as per Novartis Guidance on Standardization of Pharmacokinetic Parameters. The linear trapezoidal rule will be used for AUC calculation. Regression analysis of the terminal plasma elimination phase for the determination of T1/2 will include at least 3 data points after Cmax. If the adjusted R² value of the regression analysis of the terminal phase will be less than 0.75, no values will be reported for T1/2, AUCinf and CL/F.

In addition to non-compartmental methods, individual compartmental modelling (Phoenix WinNonlin, version 6.2 or higher) may be used to derive individual estimates of oral drug clearance (CLss/F) as well other model-derived parameters such as absorption rate constant and volume of distribution.

5.2 Descriptive analyses

The pharmacokinetics of CDZ173 will be evaluated in patients in the PK analysis set. CDZ173 plasma concentration data will be listed by treatment, patient, and visit/sampling time point. Descriptive summary statistics will be provided by treatment and visit/sampling time point.

Commercially Confidential Information Summary statistics will include mean (arithmetic and geometric), SD, CV (arithmetic and geometric), median, minimum and maximum. Commercially Confidential Information A geometric mean will not be reported if the dataset includes zero values.

Pharmacokinetic parameters will be calculated and will be listed by treatment and patient. Summary statistics will include mean (arithmetic and geometric), SD, CV (arithmetic and geometric), median, minimum and maximum. An exception to this is Tmax where median, minimum and maximum will be presented.

Arithmetic mean (SD) profiles and geometric mean (95% CI) for plasma concentration-time data (day 1) and Ctrough versus Visit (multiple dose) data will be plotted over time.

Overlaying individual plasma concentration-time profiles (day 1) as well as for Ctrough-visit (after multiple dose) will be generated along profiles for individual subjects.

Commercially Confidential Information

5.4 Pharmacokinetic / pharmacodynamic interactions

Relationships between exposure and selected PD or biomarker variables will be explored by a graphical approach and descriptive statistics of exposure and PD or biomarker variables will be provided. Additional analysis such as exposure-response models will be performed, if warranted.

6 Statistical methods for primary efficacy parameters

6.1 Primary objective

The primary aim of Part II is to assess efficacy of CDZ173 at the selected dose (70 mg b.i.d.) after 12 weeks of treatment.

6.1.1 Estimands

Commercially Confidential Information

6.1.2 Variables

Index lesions will be selected from measurable nodal and extranodal lesions as per the Cheson methodology (Cheson et al 1999). A maximum of six of the largest dominant lesions should be selected and documented at baseline and assessed again at the end of treatment (i.e. the Day 85 assessment for patients who complete the 12 week treatment period or the treatment discontinuation visit for patients who discontinue treatment prematurely prior to Day 85 visit). The percentage of naïve B cells is assessed at baseline, Day 1, Day 29, Day 57 and Day 85, and at the discontinuation visit for patients who discontinue treatment prematurely prior to Day 85 visit. The co-primary variables to assess efficacy in Part II will be the change from baseline in the log10-transformed sum of the products of diameters (SPD) of the index lesions and the change from baseline in the percentage of naïve B cells out of total B cells, see [Section 8.3](#) for details of the read-out names for all biomarkers.

